#### Exploratory Generalization Measure

Generalization measures will be examined in a tertiary analysis to explore whether treatment effects generalize to everyday activities or participation in the community. Based on our previous study, treatment effect did not generalize to everyday activities as measured by the BRIEF-A. However, with the proposed methodological changes and the addition of functional practice with a Smartphone application, generalization to activities and community participation is anticipated to improve. The Metacognitive Index of the BRIEF-A was confirmed as a factor in our previous factor analysis and represents the executive function components targeted by GMT. The BRIEF-A was selected over the recommended common data element measure, the Frontal Systems Behavior Scale (FrSBe); since the FrSBe has not been tested in a homogenous TBI sample. While, our previous study did not reflect a significant improvement at the activity level, we will conduct a tertiary analysis to detect generalization using the BRIEF-A. In addition to the activity level of executive function, we would like to determine the effect of treatment at the community participation level. The TBI Outcomes Workgroup on common data elements (Wilde, 2010) has recommended the PART-O to measure participation in the community.

Behavior Rating Inventory of Executive Functions–Adult (BRIEF-A) is a self and informant report questionnaire consisting of 75 statements about executive behaviors. There are three possible responses to items: often, sometimes, never. There are nine subscales: inhibit, self-monitor, plan/organize, shift initiation, task monitor, emotional control, working memory, and organization of materials. Normative self-report (n=1,050) reliability ranges from .73 to .90 for the scales and .93 to .96 for Index and Global Executive Composite scores. While the reliability in a mixed clinical sample (n=233) ranged from .80 to .94 for scales and .96 to .98 for Index and Global Executive Composite scores. Test-retest reliability over 4 weeks averaged .82 to .93 on the scales and .94 for Index and Global Executive Composite

scores. The total BRIEF-A score correlates at .84 with the Dysexecutive Questionnaire (Roth, 2005). In a sample of patients diagnosed with TBI, the MI reported a Cronbach alpha of 0.96 (Waid-Ebbs et al., 2012). The Metacognitive Index of the score of the BRIEF-A will be used to detect a change of executive functioning in the subject's home environment.

Community Reintegration of Service Members (CRIS): will be used to measure participation. The CRIS was developed specifically for soldiers with disabilities (Resnik et al., 2009, 2011) and is available in two formats, a paper and pencil version with 128 items and a computer adapted version that takes no more than 10 minutes to complete. Three scales are found in the CRIS and have good internal reliability: Extent of Participation = 0.91, Perceived Limitations = 0.93, and Satisfaction with Participation = 0.97 (Resnik et al, 2009). Meaningful detectable change indices were 5.9, 6.2, and 3.6, respectively for Extent, Perceived and Satisfaction subscales (Resnik et al, 2012). CRIS-CAT scores were predictive of SF-12 physical and mental health related quality of life scores at the 1-year follow-up (Resnik et al, 2012). Preliminary analysis described reveals good internal reliability and separation into ability levels in a sample of 44 mTBI Veterans. Test Retest reliability is 0.95 for Extent of participation; 0.85 for Perceive limitation; and 0.95 for Satisfaction scales.

## **7. Statistical Methods**

### Statistical Analysis Plan

Participants, who attend less than 90% of the treatment sessions, have medication changes during treatment that affect cognition and/or receive more than 5 hours of therapy (other than GMT) from a mental health specialist during the study will not be included in the final analysis.

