## **6. Research Plan:**

To determine the effect of GMT on veterans with mTBI the following research will be conducted. Clinical staff from the NF/SG VHS will hand out recruitment flyers or refer OEF/OIF/ONF veterans diagnosed with mTBI to the Principal Investigator. Referred Veterans will be contacted by the PI or interested Veterans will contact the PI. Veterans that meet the inclusion/exclusion criteria will be scheduled to obtain consent. Once

consent has been obtained the veteran will be scheduled for the first screening visit. Veterans that meet inclusion criteria will be randomly assigned to either treatment or control groups, in a ratio of 38:16. In addition, the Pocock-Simon covariate adaptive randomization procedure will be used so that, for each PTSD severity category within each of the two sites, approximately 70% (38/54) of subjects are assigned to treatment group; consequently, there will be approximately equal proportion of PTSD subjects assigned to the treatment and control groups within each of the two study sites. Each veteran will complete testing prior to a 10-week intervention or control period; after intervention or control period; and at a one-month follow-up. Intervention will be offered to participants in the control group once testing is complete.

Participants will also be recruited and run in a parallel study in Durham under a Durham VA IRB approval. A total of 168 participants are anticipated to be enrolled in both Gainesville and Durham. Data from Durham will be entered in a VA share drive that both Gainesville and Durham staff can access. Data will not be transferred.

Table # 2 Study Design

	1 st Measure	GMT/Wait	2 nd Measure	3 rd Measure
Group A (n=38)	Pre-treatment testing	GMT/FP 10 wks	Post-treatment testing	Follow-up testing
Group B (n=16)	Pre-Control testing	Control (Brain Health Workshop) 10 wks	Post-control testing	Follow-up Control testing

Methods

Subjects

*Proxy/Informant: patient will select a person to answer a questionnaire on their executive function that observes the patient at least 2-3 times a week and is at least 18 years of age.*

Patient Inclusion Criteria:

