- Diagnosis of Mild TBI or concussion by a physician or neuropsychologist in the medical record compliant with the American Congress of Rehabilitation Medicine; any of three following criteria are met: 1) loss of consciousness less than 30 minutes with a Glasgow Coma Scale of 13 or above; 2) any loss of memory for events immediately before and after the event (not longer than 24 hours); any alteration of mental state at the time of accident; 3) any focal neurological deficits that may, or may not, be transient (ACRM, 1993).
- Executive dysfunction determined by at least 1.5 standard deviation below the average scaled score (corrected for age) on either the Delis-Kaplan Executive function System (D-Kefs) Color Word Interference Test, or the EXAMINER flanker task.
- Age 18 to 55 years
- At least 4 months post injury
- Family member or friend that is willing to provide feedback

Exclusion Criteria:

- History of pre-morbid learning disability
- History of psychiatric diagnosis sufficiently severe to have resulted in inpatient hospitalization.
- Neurological disease unrelated to TBI (seizure disorder, stroke, ADHD)
- Score < 90 on National Adult Reading Test (NART)
- Failure of validity testing on either the Test of Memory Malinger (TOMM),. Score of 45 or less on TOMM Trial 2 or retention trial.
- Reported alcohol or substance abuse within the past year
- Reported involvement in current litigation
- Recent change of medications for seizures, depression or memory.
- Currently enrolled in other cognitive therapy that cannot be discontinued
- Does not speak English fluently
- Not competent to provide consent (also, not able to demonstrate understanding of expectations of study and potential risks of participation).

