### **Aim 1.**

**Aim 1 is to test the benefits of GMT for improving executive function.**

Hypothesis 1a: GMT and home practice device will significantly improve problem solving ability compared to the control group (primary measure: time to completion on the Tower of London (cTOL). Since PTSD is prevalent and a potentially influencing co-morbidity, we will investigate whether there is a significant interaction between treatment group and PTSD severity. Secondary measures include number of optimal moves on the TOL; and measures derived from the Stop Signal Task (SST; a measure of inhibition control).

Exploratory Hypothesis 1.b. GMT and functional practice will significantly improve everyday activities that require executive function skills (primary measure: Behavior Rating Inventory of Executive Function-Adult version, secondary measure: CRIS).

**Analysis Plan for Hypothesis 1.a. and Hypothesis 1.b.** To test the first specific aim (hypothesis 1a), the primary analysis will use two sample t-test to compare group A (intervention) and group B (control) on improvements in time to completion on the TOL. In addition, as an exploratory analysis, we will perform a regression analysis that includes treatment group, PTSD severity and their interaction as independent variables, to adjust for PTSD severity and to investigate whether there is interaction between treatment group and PTSD severity. Similar analyses will be performed for hypothesis 1 for secondary outcome variables of changes in index of optimal moves on the TOL and reaction time (RT) and accuracy on SST. To test hypothesis 1b, exploratory *tertiary analysis* using paired t-tests will determine whether treatment effect generalizes to executive function performance in everyday activities (BRIEF-A) or engagement in community participation (CRIS).

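### The only planned comparison of GMT with control drops randomised participants for post-randomisation reasons, with no all-randomised analysis, so its estimate can be biased in either direction

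*Combined protocol and SAP*

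**What the plan says.** The first paragraph of the Statistical Analysis Plan (Section 7) sets the analysis population by exclusion. It names "Participants, who attend less than 90% of the treatment sessions, have medication changes during treatment that affect cognition", and those who "receive more than 5 hours of therapy (other than GMT) from a mental health specialist"; anyone meeting one of these conditions "during the study will not be included in the final analysis".

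Section 6 (Research Plan) puts randomisation before the treatment period: eligible veterans "will be randomly assigned to either treatment or control groups, in a ratio of 38:16". It also schedules outcome testing for everybody: "Each veteran will complete testing prior to a 10-week intervention or control period; after intervention or control period; and at a one-month follow-up".

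Under Aim 1 (Sections 5 and 7), "the primary analysis will use two sample t-test to compare group A (intervention) and group B (control") on improvement in TOL time to completion. The exploratory companion is "a regression analysis that includes treatment group, PTSD severity and their interaction as independent variables".

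The published text describes no all-randomised set, no sensitivity analysis and no treatment of missing outcomes. The Aim 2 regression refers to participants as assigned, but it is confined to the intervention arm and does not compare the arms.

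**The concern.** Attendance, a change in cognition-affecting medication, and extra mental-health care all happen after allocation. Each may be a consequence of the arm or of how the participant is doing. Selecting on them gives up the comparability that randomisation, with the Pocock-Simon balancing on PTSD severity and site, was meant to provide. Section 6 already screens on similar grounds before randomisation ("Recent change of medications for seizures, depression or memory", and concurrent cognitive therapy), where this does no harm to the comparison. The exploratory regression adjusts for PTSD severity only, so it cannot repair selection on anything else.

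The rule is also not clearly symmetric. Section 7 does not say whether Brain Health Workshop sessions count towards attendance, or how workshop contact is treated under the 5-hour limit. Section 6 says the workshop was built to match GMT in session length and facilitator contact, but that does not define the rule for controls. If the attendance criterion acts on GMT alone, selected GMT participants are compared with less selected controls.

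At stake is the study's main result, and with it the sizing of the future randomised trial announced in the Abstract.

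**Working it through.** The plan gives no absence rate, SD, effect size, alpha or power, so it has no figure of its own to reproduce. What follows is illustration. Two-sided 5% is assumed throughout.

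**Inputs from the documents.** 38 GMT and 16 control (Section 6, Table 2); 10 GMT sessions (Section 6, Procedures); the 90% threshold (Section 7). One missed session gives 9/10 = 90% and the participant stays; two give 80% and the participant is excluded.

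**Assumptions.** Sessions are missed independently with probability q. Kept and excluded GMT participants differ by 0.5 SD in mean improvement. Control exclusion is not selective.

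**Step 1, share excluded for attendance.** e = 1 − (1−q)^10 − 10q(1−q)^9. If one missed session could be made up (not stated in the documents), e is the probability of missing three or more.

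**Step 2, bias.** In each arm the mean of all randomised is (1−e) × kept + e × excluded, so the kept mean differs from it by e × (kept − excluded). Bias in the comparison = e(GMT) × gap(GMT) − e(control) × gap(control).

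**Step 3, rejection rate with no true all-randomised effect.** Noncentral t, with SE = √(1/n1 + 1/n2) in SD units.

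| q | e | e, one make-up | Kept, if rule applies to both arms | Bias (e × 0.5) | Rejection rate |
|---|---|---|---|---|---|
| 5% | 8.6% | 1.2% | 35 vs 15 | 0.04 SD | 5.2% |
| 10% | 26.4% | 7.0% | 28 vs 12 | 0.13 SD | 6.6% |
| 15% | 45.6% | 18.0% | 21 vs 9 | 0.23 SD | 8.6% |

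The sign of the bias follows the sign of the gap. At q = 10%:

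- Gaps of 0.25 and 0.75 SD give 0.264 × 0.25 = 0.07 and 0.264 × 0.75 = 0.20 SD.
- One make-up gives 0.070 × 0.5 = 0.04 SD.
- Equal gaps and equal shares in both arms give 0.
- If the rule applies to GMT only, the kept set is 28 vs 16, with SE √(1/28 + 1/16) = 0.313 and a rejection rate of 7.0%.

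**Step 4, scale.** At 28 vs 12, SE = √(1/28 + 1/12) = 0.345 and 0.132/0.345 = 0.38 of a standard error. Sampling error is therefore larger than the bias in one trial of this size, but bias does not shrink as numbers grow.

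**Step 5, cross-check by simulation.** 38 vs 16, no true effect, 40,000 runs. Exclusion is linked to improvement by a latent correlation of 0.5 unless stated. Positive bias favours GMT.

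| Excluded | Bias (SD) | Rejection rate |
|---|---|---|
| None | 0.00 | 5.1% |
| 20% of GMT, poor improvers | +0.17 | 9.1% |
| 20% of GMT, good improvers | −0.17 | 9.1% |
| 20% in each arm, opposite selection | ±0.35 | about 19% |
| 20% in each arm, same selection | 0.00 | 5.2% |
| 20% of GMT, unrelated to outcome | 0.00 | 4.7% |

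**Step 6, precision.** The difference detectable with 80% power at q = 10% is 0.99 SD on the kept set (28 vs 12), or 0.90 SD if only GMT is affected (28 vs 16). With all randomised it is 0.85 SD if every excluded participant has a post-treatment TOL (38 vs 16), 0.91 SD if half do (33 vs 14), and 0.99 SD if none do. This is not a power argument. If the kept-set effect is 0.85 SD and 0.13 SD of that is bias, power is 67% at 28 vs 12, against 66% for the smaller effect of 0.72 SD at 38 vs 16.

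**The case against.** Section 5 calls this a Phase I study of a manualised treatment. The effect in people who actually received it, free of new medication or outside therapy, is a fair early-phase question, and the rule is prespecified. On that view the gap is only a missing companion analysis, and which analysis is primary is a choice of estimand. The numbers are assumed and modest: the lead case is 0.38 of a standard error, and the bias vanishes if selection is alike in both arms, which a contact-matched control makes plausible. Only attendance is modelled; medication change and outside therapy carry no figures, and the entry screens may make them less common. The 28 vs 12 base also assumes that the workshop has 10 countable sessions, which is not stated.

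Much of this stands as a limit on size. It does not remove the problem. A per-protocol estimate is reasonable as one analysis; here it is the only one, and the plan contains nothing from which a reader could judge the selection. Similar attendance in the two arms is plausible but not assured, and similar attendance does not mean that the same kinds of people drop out. The 28 vs 16 base leads to the same conclusion.

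**Conclusion.** The concern holds and must be fixed before analysis. As written, the sole primary comparison is not protected by randomisation. This follows from the text and depends on none of the illustrative figures. The direction of bias cannot be told from the documents: it is upward if excluded GMT participants improved less, downward if they improved more or if excluded controls improved less, and nil if exclusion is unrelated to outcome or equally selective in both arms. Under the binomial assumptions, with selection in GMT only and a 0.5 SD gap, it is 0.04 to 0.23 SD. Under opposite selection in the two arms it reaches about 0.35 SD. Any such bias would carry into the planned sizing of the later trial.

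**What to change.** - Make the primary analysis all randomised participants in their assigned arm, whatever their attendance, medication changes or other therapy.
- Seek the scheduled post-treatment TOL from everyone, including those who stop attending.
- State a missing-outcome method that suits 54 participants: the planned t-test on all randomised participants with a post-treatment TOL, plus a sensitivity analysis that shifts the mean of those missing by a stated range (for example up to 0.5 SD, in either direction, in one arm and then in both) and reports where the conclusion changes.
- Keep the present Section 7 set as a labelled per-protocol analysis. Define each criterion for both arms, including whether workshop sessions count as treatment sessions and how workshop contact is treated under the 5-hour limit.
- Report exclusions by arm and reason.

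The cost is mostly wording, plus the effort of bringing disengaged participants back for a test that Section 6 already plans. The all-randomised estimate may be smaller than the per-protocol one. The t-test on observed outcomes still assumes that those without a TOL resemble the rest of their arm. The shift analysis examines that assumption: for example, 4 of 38 GMT outcomes missing with a 0.5 SD shift moves the estimate by 4/38 × 0.5 = 0.05 SD.

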### **Aim 1.**

**Aim 1 is to test the benefits of GMT for improving executive function.**

Hypothesis 1a: GMT and home practice device will significantly improve problem solving ability compared to the control group (primary measure: time to completion on the Tower of London (cTOL). Since PTSD is prevalent and a potentially influencing co-morbidity, we will investigate whether there is a significant interaction between treatment group and PTSD severity. Secondary measures include number of optimal moves on the TOL; and measures derived from the Stop Signal Task (SST; a measure of inhibition control).

Exploratory Hypothesis 1.b. GMT and functional practice will significantly improve everyday activities that require executive function skills (primary measure: Behavior Rating Inventory of Executive Function-Adult version, secondary measure: CRIS).

**Analysis Plan for Hypothesis 1.a. and Hypothesis 1.b.** To test the first specific aim (hypothesis 1a), the primary analysis will use two sample t-test to compare group A (intervention) and group B (control) on improvements in time to completion on the TOL. In addition, as an exploratory analysis, we will perform a regression analysis that includes treatment group, PTSD severity and their interaction as independent variables, to adjust for PTSD severity and to investigate whether there is interaction between treatment group and PTSD severity. Similar analyses will be performed for hypothesis 1 for secondary outcome variables of changes in index of optimal moves on the TOL and reaction time (RT) and accuracy on SST. To test hypothesis 1b, exploratory *tertiary analysis* using paired t-tests will determine whether treatment effect generalizes to executive function performance in everyday activities (BRIEF-A) or engagement in community participation (CRIS).

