### *Procedures*

Intervention: The GMT is a 7-session intervention has been modified to a 10-session (2 hours/ session) interactive Power Point module that is presented in an individual or group format. Sessions 5, 6 and 7 have been split into two sessions each with time added to set-up and review functional practice. If a group format, the subject will be incorporated into a therapy session with 3-5 other participants (either other clinical patients or research participants diagnosed with TBI). During each session, a 5-stage strategy is taught to the participants. The 5-stage process consists of “stop-what am I doing?”, “define the goal”, “list the steps”, “learn the steps” then “check-am I doing what I planned”. The strategy is then incorporated into tasks practiced in the group session as well as in tasks each participant is to practice at home. The participants discuss utilization of the strategies and support the other members in the group. Friends or family members will participate in a training session prior to beginning GMT with the subject. The family member will be called each week during the GMT and asked to report whether the subject had an easy or difficulty time completing the homework assignments each week.

*Simulated Practice In The Laboratory:* Tasks during GMT training include exercises such as: 1) clapping to words while inhibiting clapping to a targeted word; 2) card sorting; 3) decision making and planning in order to complete five activities within a four minute time span; 4) Catalog Task; and 5) Book keeping task. The exercises start with relatively easy tasks and progress to more complex tasks. Participant’s strengths and weaknesses are discussed. Improvements are identified and reinforced as they learn more efficient planning and problem solving. The following steps are taught during simulated tasks: 1) Identify Main Goal; 2) Break down task into sub-goals and steps for each goal; 3) List supplies needed; 4) Recognize potential barriers to completing goal; 5) Determine strategy to accomplish task; 6) Prepare to begin task with “presence of mindedness” exercise; 7) State goal out loud; 8) Begin task and stop self frequently to state main goal out loud and check to be sure one is working toward the goal (on target).

*Functional Practice with Smartphone Technology:* In addition to GMT in the lab, three tasks will be first practice in the lab, than practiced at home. Participants will

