Primary Outcome Measure: Tower of London (TOL): is a computerized program in which patients are shown two pictures simultaneously of a goal board and a test board (Unterrainer et al, 2006). Each picture shows three balls of different colors arranged on three pegs, with the balls in a unique arrangement in each picture. Patients are instructed to determine the fewest possible moves of the balls in the test picture to make the

arrangement of balls identical to that of the goal picture within 60 seconds. The screen reports whether the response is correct or incorrect. Test administration is less than 45 minutes for each session (pre/post/follow-up). Each set consists of 70 problems of variable difficulty, determined by variables, such as, the number of moves needed to solve the problem (Berg and Byrd, 2002). In turn, each set consists of the same number of 4, 5, 6 or 7 move problems and has the same average difficulty level. Difficulty rating is based on global and specific problem parameters shown to affect the planning process (Kaller, 2007, 2008, 2009; Berg, Byrd, McNamara, & Case, 2010; Kaller, Unterrainer, Rahm, & Halsband, 2004). The dependent variables are the total time spent solving the problem and the optimal moves made toward the goal display.

Based on our previous studies, executive function represents three factors (behavior regulation, emotional regulation and metacognition) (Waid, Wen, Heaton, andVELOZO, submitted to Neuropsychology). GMT is a metacognitive training with emphasis on planning prior to engaging in a complex task. Therefore, a primary measure that captures the planning and problem solving of a multi-step task, called the Tower of London (TOL), was selected. Based on results from our preliminary study, the dependent variables of total time and optimal moves will be used to determine treatment effect. While, not all of the participants in our previous work demonstrated significant improvement on these variables, group differences based on paired T-tests were significant in Total Time ( $p=0.026$ ) and Optimal Moves ( $p=0.022$ ) from baseline to treatment. In addition to our findings, Levine (2011) demonstrated a significant change in the TOL following GMT for a mixed neurological sample compared to a control group. Thus, the TOL appears to be sensitive to the effects of GMT.

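### The primary t-test on change in TOL time ignores the randomisation factors and fixes the baseline slope at 1; an adjusted model would usually be more precise at almost no cost

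*Combined protocol and SAP*

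**What the plan says.** - **Primary test.** Section 7 (Statistical Methods), Aim 1, states for the TOL that "the primary analysis will use two sample t-test to compare group A (intervention) and group B (control) on improvements in time to completion". Section 5 (Specific Aims) names the same test. Neither lists a covariate.
- **Allocation.** Section 6 (Research Plan) randomises "in a ratio of 38:16". It says that "the Pocock-Simon covariate adaptive randomization procedure will be used so that, for each PTSD severity category within each of the two sites", a fixed share goes to the GMT arm, and it gives that share as "approximately 70% (38/54) of subjects are assigned to treatment group".
- **Baseline TOL.** Section 6 has every veteran tested before the 10-week period. Table 1 (Testing Schedule) lists the TOL at the pre-treatment, post-treatment and one-month visits.
- **The only between-group regression in Aim 1.** It is labelled exploratory: a "regression analysis that includes treatment group, PTSD severity and their interaction as independent variables, to adjust for PTSD severity". It lists neither site nor baseline TOL.
- **The plan's view of PTSD.** The interaction is introduced with the words "Since PTSD is prevalent and a potentially influencing co-morbidity". Hypothesis 2 then expects PTSD, among other factors, to affect response to treatment, with TOL time as the dependent variable.

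The plan gives no reason for leaving the balancing factors out of the primary test.

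**The concern.** Two separate matters are involved.

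1. **Randomisation factors left out.** Balancing on site and PTSD category removes most of their contribution to chance differences between the arms. A t-test that ignores them still counts their between-stratum variation in its standard error. To the extent that they predict change in TOL time, the standard error is too large, the test is conservative and the interval is too wide. If they do not predict change, nothing is distorted.
2. **Baseline slope fixed at 1.** The change score does use baseline TOL, and its standard error is valid in this respect. Estimating the slope is generally more efficient. The gain disappears when the regression slope of post on baseline equals 1.

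Power and interval width are at stake, not bias. With 16 controls precision is limited, and the abstract says the study is meant to size a later randomised trial.

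**Working it through.** **Inputs from the documents.** 38 and 16 participants (38/54 = 70.4%, which agrees with the stated 70%); two sites; PTSD severity categories, number not stated; TOL before and after treatment. The documents give no alpha, power, effect size, SD or baseline-to-post correlation, so there is no sample-size figure to reproduce.

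**Assumptions.** Two-sided 5% test, 80% power, 54 analysed (before the exclusions in section 7). Baseline SD is 1 and post SD is k; rho is the baseline-to-post correlation; R2 is the share of variance in change explained by site and PTSD.

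**Step 1: detectable effect at 38 v 16.** The standard error multiplier is sqrt(1/38 + 1/16) = 0.298. By the noncentral t, the detectable difference is 0.851 SD of the analysed variable on 52 df (t-test). It is 0.852 on 49 df (arm, baseline, site, two PTSD categories). The three lost degrees of freedom cost almost nothing.

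**Step 2: estimating the baseline slope.**
- Variance of change: 1 + k² − 2·rho·k.
- Residual variance after baseline adjustment: k²(1 − rho²).
- At k = 1 their ratio is (1 − rho²)/(2 − 2·rho) = (1 + rho)/2. The interval ratio is its square root.
- Detectable effect in baseline SDs: 0.851·sqrt(2 − 2·rho) for the t-test, 0.852·sqrt(1 − rho²) for the adjusted model.

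| rho (k = 1) | Interval ratio | Interval narrower by | Detectable, t-test | Detectable, adjusted |
|---|---|---|---|---|
| 0.5 | 0.87 | 13% | 0.85 | 0.74 |
| 0.7 | 0.92 | 8% | 0.66 | 0.61 |
| 0.8 | 0.95 | 5% | 0.54 | 0.51 |
| 0.9 | 0.97 | 3% | 0.38 | 0.37 |

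No-gain case: with k = 1.25 and rho = 0.8 the slope is 0.8 × 1.25 = 1. Both variances are then 0.5625 (1 + 1.5625 − 2, and 1.5625 × 0.36).

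**Step 3: leaving out site and PTSD.** With perfect balance the t-test's standard error is too large by a factor 1/sqrt(1 − R2). The true rejection rate is then the two-sided tail beyond 2.007/sqrt(1 − R2) on 52 df. Real balance is imperfect, so Pocock-Simon allocation was also simulated (two binary factors, 0.9 biased coin, 6,000 runs per cell, Monte Carlo error about ±0.6 points).

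| R2 | Perfect balance: SE factor | Perfect balance: type I | Simulated, t-test | Simulated, adjusted |
|---|---|---|---|---|
| 0 | 1.00 | 5.0% | 5.6% | 5.7% |
| 0.1 | 1.05 | 3.9% | 3.7% | 4.8% |
| 0.2 | 1.12 | 2.9% | 3.2% | 5.0% |
| 0.3 | 1.20 | 2.0% | 2.3% | 5.5% |

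Across the allocation variants run, the t-test's standard error was overstated by about 0%, 4–5%, 8–11% and 14–18% at these R2 values. A 0.8 coin, three PTSD categories, or balancing within site-by-PTSD cells left the t-test's type I error between 4.0% and 4.5%, 2.7% and 3.4%, and 2.1% and 2.6% at R2 of 0.1, 0.2 and 0.3.

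**Step 4: both together.** Simulated power (4,000 runs, k = 1), with the effect set so that the t-test has 80% power at R2 = 0:

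| rho | R2 = 0: t-test v adjusted | R2 = 0.1: t-test v adjusted |
|---|---|---|
| 0.5 | 81% v 90% | 76% v 88% |
| 0.7 | 82% v 86% | 77% v 85% |
| 0.8 | 80% v 83% | 77% v 83% |
| 0.9 | 82% v 82% | 77% v 81% |

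Least favourable case (k = 1.25, rho 0.8, R2 = 0): 81% v 80%, with the adjusted interval 1.3% wider.

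**The case against.** The strongest reply is that nothing is invalid. A prespecified t-test on change is an accepted analysis and already uses baseline TOL, and the study is described as Phase I. That stands: this is a point about efficiency, not the correction of an error.

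Further points on that side:

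- **The size is unknown.** True. Neither rho nor R2 is in the documents, and the grid runs from a clear gain to a slight loss. No single cell should be read as the expected result.
- **The remark about PTSD introduces an interaction, not a prognostic effect.** True of that sentence. The same section, however, plans a regression whose stated purpose includes adjusting for PTSD severity. Nothing in the documents suggests that site predicts change.
- **The exploratory regression already adjusts for PTSD.** In part. It is not primary and lists neither site nor baseline TOL. With the interaction included and PCL-M entered uncentred, the arm coefficient is the effect at a score of zero, outside the scale's 17–85 range.
- **The 1% cost assumes all 54 are analysed.** Section 7 excludes participants for low attendance, medication changes or other therapy, at a rate it does not predict. With an assumed 30% excluded (about 11 controls left), the least favourable case becomes an interval about 3% wider and power of 60% against 63%. With exclusions of 20–40%, rho 0.7 and R2 of 0.1 to 0.3, the adjusted interval was still 9–21% narrower.

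These points limit the claim, but they do not remove the imbalance between a small possible loss and a larger possible gain.

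**Conclusion.** The concern holds. The planned primary test is valid but discards precision that the design and the collected data make available. Under the assumptions shown, estimating the baseline slope narrows the interval by 3% to 13% when pre and post SDs are equal. Ignoring the balancing factors makes the test conservative if they are prognostic: about 4%, 3% and 2% true type I error at R2 of 0.1, 0.2 and 0.3. At rho 0.7 and R2 0.1, the two together move simulated power from 77% to 85%. If no covariate helps, the cost is about 1% in interval width at 54 analysed, or about 3% with an assumed 30% excluded. The change is recommended, not essential. Confidence is moderate, because rho, R2, the biased-coin probability and the number of PTSD categories are not given.

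**What to change.** Before outcome data are seen by arm, change section 7 and the matching text in section 5 as follows:

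- **Primary analysis:** a linear model of post-treatment TOL time on arm, baseline TOL time, site and the PTSD severity category used in randomisation. Report the arm coefficient with its 95% confidence interval. Name the visit, since the plan does not say whether improvement is measured to the post-treatment or the one-month test; post-treatment is assumed here.
- **Sensitivity analysis:** the two-sample t-test on change.
- **Interaction:** a separate exploratory model with the arm-by-PTSD term, and PCL-M centred at its mean if entered as a score.
- **Secondary outcomes:** the same adjusted model for optimal moves and the Stop Signal Task measures.

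**Cost.** SAP wording, including a definition of the PTSD categories, which section 6 uses without cut-points. No new data are needed. Three degrees of freedom are spent with two PTSD categories (52 to 49), and one more for each further category.

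**Not addressed.** Section 6 (Procedures) says that, in the group format, "the subject will be incorporated into a therapy session with 3-5 other participants". Clustering from shared sessions is a separate issue that acts in the opposite direction, and this change does not deal with it.
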